2 DEFINITION OF EVALUABLE PATIENTS

2.1 Patients evaluable at enrolment (FULL ANALYSIS SET)

All enrolled patients meeting the following inclusion / exclusion / other criteria listed in the present paragraph will be considered evaluable at enrollment (Full analysis set) (i.e. COPD patients aged ≥ 40 years, with stable pharmacological treatment for COPD and no exacerbations for at least 3 months, who signed informed consent and privacy form, with at least one Treatment Satisfaction Questionnaire for Medication (TSQM-9) domain score calculated at enrollment visit):

Inclusion criteria

Criterion 1: Patients aged ≥ 40 years

- Question "1. Is the patient aged ≥ 40 years?" = "Yes" [\[F01_INC_EXC_CRITERIA.CI_1\]](#) AND
- Inclusion criterion "1. Patients aged ≥ 40 years?" not checked in the PROTOCOL DEVIATION FORM [\[F24_PROTOCOL_DEVIATION_FORM.PD_CI_1\]](#) AND
- Age at enrollment visit (years) ≥ 40 [\[_PatientInfo.Age\]](#)

Criterion 2: Patients must have a documented diagnosis of chronic obstructive pulmonary disease (COPD)

- Question "2. Has the patient a documented diagnosis of chronic obstructive pulmonary disease (COPD)?" = "Yes" [\[F01_INC_EXC_CRITERIA.CI_2\]](#) AND
- Inclusion criterion "2. Patients must have a documented diagnosis of chronic obstructive pulmonary disease (COPD)" not checked in the PROTOCOL DEVIATION FORM [\[F24_PROTOCOL_DEVIATION_FORM.PD_CI_2\]](#) AND
- Date of COPD diagnosis (mm/yyyy) not missing [\[F04_COPD_MEDICAL_HISTORY.MH_Date_diagnosis\]](#)

Criterion 3: Patients with no exacerbations in the last 3 months

- Question "3. Patient without any exacerbation in the last 3 months" = "Yes" [\[F01_INC_EXC_CRITERIA.QUESTION_3.CI_3\]](#) AND
- Inclusion criterion "3. Patients with no exacerbations in the last 3 months" not checked in the PROTOCOL DEVIATION FORM [\[F24_PROTOCOL_DEVIATION_FORM.PD_CI_3\]](#) AND
- Onset dates at each follow-up visit (Row 1 to 10) [\[F08_EXACERBATIONS.Ex_exacer_1-10_onset_date\]](#) > Date of enrolment visit (dd/mm/yyyy) [\[_PatientInfo.Date_enrollment\]](#)

Criterion 4: Patients requiring regular treatment according to GOLD guidelines, i.e.: undergoing stable pharmacological treatment for COPD since at least 3 months

- Question "4. Does the patient require a regular treatment according to GOLD guidelines, i.e.: undergoing stable pharmacological treatment for COPD since at least 3 months?" = "Yes" [\[F01_INC_EXC_CRITERIA.CI_4\]](#) AND

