The Morisky medication Adherence Scale 4 items (MMAS-4) is a self-reported, medication-taking behavior scale and consists of four questions about the way patients might experience drug errors or omissions. Each item [F13_MMAS_4.MMAS_4_1 - MMAS_4_4] has a scoring scheme of "Yes" = 0 and "No" = 1. Items are summed to give a non-adherence score ranging from 0 to 4; a higher score means better adherence to therapy (Morisky DE, Green LW, Levine DM. Concurrent and predictive validity of a self-reported measure of medication adherence. *Med Care*. 1986 Jan;24(1):67-74).

The score can be calculated if at least 3 out of 4 of the items are completed. If only one item is omitted, the value for the missing item is the group median of this item that has been completed by all eligible participants. This median value will be imputed for all eligible cases who did not answer this item.

Changes in the MMAS-4 score at each follow-up visit from enrollment will be calculated, for each patient, as the following difference: (score at 6/12 months - score at enrollment), if both scores are available.

COPD pharmacological treatments (classes) ongoing at enrollment

All COPD pharmacological treatments having "End date of therapy" [F20_COPD_PHARMACOLOGICAL_THERAPY.END_DATE_THER] > "Date of enrollment visit" [PatientInfo.Date_enrollment] OR ("End date of therapy" missing and "Ongoing at the end of observation?" [F20_COPD_PHARMACOLOGICAL_THERAPY.ONGOING_THER] = "Yes").

Drug names will be coded by CDM and grouped according to the following categories:

- LAMA alone
- LABA alone

- ICS alone
- LABA + LAMA (Fixed dose combination or not)
- LABA + ICS (Fixed dose combination or not)
- LABA + LAMA + ICS
- SABA or SAMA on demand
- Other: pharmacological therapies for COPD not included in the previous classes.

Categories above are not mutually exclusive: a patient could be classified in more than one category (i.e. if a patient is receiving LABA and SABA on demand, [REDACTED] will be classified both in the “LABA alone” and in the “SABA or SAMA on demand” classes). Only therapies for COPD will be considered (i.e. those records with field Therapy for [F20_COPD PHARMACOLOGICAL THERAPY.THERAPY_FOR] = “COPD”), while therapies for COPD exacerbations or for COPD-related adverse events will not be considered nor classified.

COPD pharmacological treatments (classes) ongoing at 6- and 12-month follow-up visit

At each follow-up visit, all COPD treatments classes (see algorithm above) having

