Considering only COPD pharmacological treatments (i.e. those records with field “Therapy for” [F20_COPD PHARMACOLOGICAL THERAPY.THERAPY_FOR] = “COPD”) ongoing at enrollment or started after enrollment (i.e. with “Ongoing at the end of observation?” [F20_COPD PHARMACOLOGICAL THERAPY.ONGOING_THER] = “Yes” OR with “Start date of therapy” [F20_COPD PHARMACOLOGICAL THERAPY.START_DATE_THER] > “Enrollment date”), patients who switched treatment during the observation period* will be those with more than one record with the above-mentioned characteristics in the COPD PHARMACOLOGICAL THERAPY log form, excluding therapies started the very same day according to Start date of therapy. In particular, patients switching treatment are those with at least one change in the drug/frequency/route/formulation/device of administration after enrollment (also adding / stopping a COPD treatment is a switch).

*switches occurred before enrollment will not be considered.

Number of therapies administered for COPD, COPD-related adverse events and COPD exacerbations

The **number of therapies administered for COPD per patient during observation period** will be calculated as the sum of records of the COPD PHARMACOLOGICAL THERAPY log form considering only pharmacological treatments for COPD (i.e. those records with field "Therapy for" [F20_COPD PHARMACOLOGICAL THERAPY. THERAPY_FOR] = "COPD") ongoing at enrollment or started after enrollment (i.e. with "Ongoing at the end of observation?" [F20_COPD PHARMACOLOGICAL THERAPY. ONGOING_THER] = "Yes" OR with "Start date of therapy" [F20_COPD PHARMACOLOGICAL THERAPY. START_DATE_THER] > "Enrollment date").

Similarly, the **number of therapies administered for COPD-related adverse events and COPD exacerbations per patient during observation period** will be calculated as the sum of records of the COPD PHARMACOLOGICAL THERAPY log form considering only pharmacological treatments for COPD-related adverse events and COPD exacerbations (i.e. those records with field "Therapy for" [F20_COPD PHARMACOLOGICAL THERAPY. THERAPY_FOR] = "COPD-related adverse event" OR "COPD exacerbation") ongoing at enrollment or started after enrollment (i.e. with "Ongoing at the end of observation?" [F20_COPD PHARMACOLOGICAL THERAPY. ONGOING_THER] = "Yes" OR with "Start date of therapy" [F20_COPD PHARMACOLOGICAL THERAPY. START_DATE_THER] > "Enrollment date").

Exacerbations during the observation period

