- **Table 38. Exacerbations: patients' distribution:** Table output will be verified by another BS or CDM ; moreover, randomly chosen patients (20% of evaluable patients) will be checked by a CDM or another BS in order to assess whether Number of exacerbations per patient during observation period is correctly computed according to the algorithm described in the SAP
- **Table 40. Overall Summary of Adverse Events and Adverse Event Reactions:** Table output will be verified by another BS or CDM ; moreover, randomly chosen patients (10% of evaluable patients) will be checked by a CDM or another BS in order to assess whether patients with at least one AE/SAE/ADR were correctly identified according to the algorithm described in the SAP
- **Table 43. List of adverse events:** 3 patients will be verified with respect to DB content
- **Table 45. Patients' satisfaction for medical treatment (TSQM-9 items) at each study visit - Switchers vs non-switchers:** randomly chosen patients (50% of evaluable patients) will be checked by a CDM or another BS in order to assess whether they were correctly classified as switchers/non-switchers.

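### The SAP's record-count rule for switchers contradicts its own definition and, taken literally, misclassifies patients in both directions in supportive Tables 45-46

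*SAP*

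**What the plan says.** The paragraph in SAP Section 3 on patients switching and not switching treatments contains a counting rule, a definition and a footnote.

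- **Counting rule.** The records considered are those for COPD described as "ongoing at enrollment or started after enrollment". The field conditions that follow make this concrete: the record is marked as ongoing at the end of observation, or its start date is after the enrolment date. Then "patients who switched treatment during the observation period* will be those with more than one record with the above-mentioned characteristics", with one exemption: "excluding therapies started the very same day according to Start date of therapy".
- **Definition.** The next sentence says "patients switching treatment are those with at least one change in the drug/frequency/route/formulation/device of administration after enrollment", and adds in brackets that adding or stopping a COPD treatment is also a switch.
- **Footnote.** "switches occurred before enrollment will not be considered".

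The flag is used in Tables 45 and 46, listed under supportive analysis, which show TSQM-9 items and subscales by visit for switchers and non-switchers. The text describing these two tables cannot be read in the public copy. For Table 45, SAP Section 6 plans a check of 50% of evaluable patients "in order to assess whether they were correctly classified as switchers/non-switchers".

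**The concern.** The counting rule contains no condition that anything changed. It asks how many COPD records qualify and whether they share a start date. The definition and footnote ask whether something changed after enrolment. The SAP does not say which prevails, and only the count is tied to eCRF field names, so it is the natural one to program.

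The patients on whom the two differ are expected in this study. SAP Section 3 says of its drug classes "Categories above are not mutually exclusive: a patient could be classified in more than one category", and its example is a patient on a LABA with an on-demand SABA. It also defines patients on both fixed and non-fixed therapy. Inclusion criterion 4, "undergoing stable pharmacological treatment for COPD since at least 3 months", requires drugs taken at enrolment to have started more than 3 months earlier, but not on the same day.

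At stake is the meaning of Tables 45-46. If the count is programmed, the switcher column can contain patients whose treatment never changed, and the non-switcher column can contain patients whose treatment did. A difference in satisfaction between the columns, or the lack of one, could not then be attributed to switching.

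**Working it through.** The plan gives no figure to reproduce here, so the check applies both texts to simple treatment histories.

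**Inputs (all from SAP Section 3).**
- Qualifying record: therapy for COPD, and (ongoing at end of observation = Yes, or start date > enrolment date).
- Count rule: switcher if the qualifying records have more than one distinct start date. This is the record count with same-day starts collapsed.
- Definition: switcher if any drug was added, stopped or changed after enrolment.

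**Results.** All drugs started before enrolment unless stated otherwise.

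| History | Qualifying records | Count rule | Definition | Agree? |
|---|---|---|---|---|
| One drug, unchanged | 1 | non-switcher | non-switcher | yes |
| Two drugs, same start day, unchanged | 2, one start date | non-switcher | non-switcher | yes |
| Two drugs, different start days, unchanged | 2 | **switcher** | non-switcher | **no** |
| Drug B added to A after enrolment | 2 | switcher | switcher | yes |
| A replaced by B after enrolment | 1 (B only) | **non-switcher** | switcher | **no** |
| Two drugs, one stopped after enrolment | 1 | **non-switcher** | switcher | **no** |
| Only drug stopped after enrolment | 0 | **non-switcher** | switcher | **no** |
| A to B to C after enrolment | 2 (B and C) | switcher | switcher | yes |

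The texts disagree on four of the eight histories: one false switcher and three missed switchers. These are test histories, so four of eight says nothing about how often each occurs.

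**Why the misses arise.** A drug started before enrolment and stopped before the end of observation meets neither field condition, so its record drops out. A replacement or stop is missed only when at most one qualifying record remains. If the patient also stays on another drug with a different start date, the count gives the right label, though not because it detected the change.

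**Does the wording of the filter rescue it?** The words before the field conditions refer to drugs ongoing at enrolment, not at the end of observation. On that reading drug A in the replacement row would count, as would the stopped drug in the two-drug row, and both patients would become switchers. The patient who stopped an only drug would still have one record and be missed. The unchanged patient on two separately started drugs would still have two records and be a false switcher. So the false-switcher error survives either reading, while most of the missed-switcher error comes from the field condition.

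**Cross-check within the SAP.** The next definition in Section 3, the number of therapies administered for COPD, uses the same filter. Apart from the same-day exemption, the count rule is therefore equivalent to that number exceeding one.

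**The case against.** The strongest reply is that the paragraph should be read as a whole. The definition follows as a specification of the count, and the footnote excludes earlier switches. A programmer who honours all three would class the unchanged two-drug patient as a non-switcher. This stands in part: misclassification is certain only if the count is programmed as written. It does not remove the defect, because nothing says that the definition overrides the count. The planned 50% check would probably expose the conflict, but it cannot resolve it while correct classification has two meanings.

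The second reply is that the reach is small. That stands. The flag is visibly used only in Tables 45-46. Tables 10-11 (SAP Section 4.3) and the models in Tables 17-19 (Section 4.9) do not use it, and switchers stay in those analyses.

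A reader might infer more than the documents support:

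- *That any two COPD records with different start dates make a switcher.* Only qualifying records count. A drug started before enrolment and stopped before the end of observation does not.
- *That Tables 45-46 become a comparison of multi-drug with single-product patients, and so of disease severity.* Under the count, non-switchers also include multi-drug patients with same-day starts and patients who replaced or stopped a drug. Neither document links the number of COPD drugs to severity.
- *That the contaminated share can be stated.* Let s be the share of true switchers, m the share of unchanged patients with qualifying records started on different days, and suppose every true switcher is captured. The false share of the switcher group is then (1-s)m / [s + (1-s)m]. Assuming s from 10% to 30% and m from 10% to 40%, it runs from 0.07/0.37 = 19% to 0.36/0.46 = 78%. Both inputs are invented, and the full-capture assumption is wrong for this rule, since the count misses some true switchers (which would raise the share). The width of the range shows only that the size is unknown.

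**Conclusion.** The concern holds as an internal contradiction in SAP Section 3. The record count does not implement the definition and footnote beside it. Applied literally, it makes switchers of unchanged patients with two or more ongoing COPD drugs started on different days before enrolment. It makes non-switchers of patients who replaced or stopped a drug after enrolment and are left with at most one qualifying record.

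This rests on two assumptions: that the count is what gets programmed, and that the field conditions, not the words introducing them, define a qualifying record. If the introducing words are used instead, the false-switcher error remains and the missed-switcher error narrows to stops that leave a single record. The number of patients affected cannot be derived from the documents. The visible consequence is confined to supportive Tables 45-46. The primary objective is not affected, but the correction is cheap and should be made before these tables are programmed.

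**What to change.** Replace the record count with one date-based rule and state that it governs:

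- A switcher has at least one COPD therapy record with a start date after enrolment, or with an end date after enrolment and before the end of observation.
- Records started before enrolment and still ongoing at the end of observation never count as a switch, however many there are.

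On the eight histories above, this rule agrees with the SAP's definition every time.

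Two checks go with it. First, confirm from the eCRF completion rules that a change in frequency, route, formulation or device is logged as a new or ended record. If it is not, dates alone will miss it. Second, compare the flag with the item on change of therapy and its reason, which Table 1 of the protocol schedules at visits 2 and 3, and query disagreements. The planned 50% check for Table 45 then has a single standard.

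The cost is one paragraph of SAP text and one reprogrammed flag. The start, end and ongoing fields are already collected, so no new data are needed, provided the first check is satisfied.

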| Eligibility criteria Inclusion and exclusion criteria, Informed consent and privacy form | X | | |
| Baseline information (Socio-)demographic variables: age, gender, race, geographic location, housing situation, marital status, educational and employment status | X | | |
| Weight, body mass index | X | X | X |
| Physical examination | X | X | X |
| Life Habits Smoking (yes/no, number of pack/years, smoke duration) | X | X | X |
| Medical History and concomitant diseases. - Charlson Comorbidity Index. | X | X | X |
| COPD medical history: Date of COPD diagnosis (years from diagnosis); n° of COPD exacerbations/year during the previous year to enrolment visit | X | | |
| Functional assessment Lung function test results (FEV1, FVC, FEV1 % of the predicted, RV, TLC,DLCO) according to clinical practice | X | X | X |
| CAT questionnaire | X | X | X |
| COPD Exacerbations** after enrollment Onset and resolution date Severity (mild, moderate, severe) | X | X | X |
| Disease severity (GOLD 2015 Guidelines) | X | X | X |
| Medications related to COPD, COPD exacerbations and adverse events (LABA, LAMA, SABA, SAMA, ICS/LABA, steroids, antibiotics, etc.): drug, dose, frequency, duration of therapy. - Long-Term Oxygen Therapy (liquid and/or concentrate). | X | X | X |
| Change of therapy during observation period and reason for change. | | X | X |
| Non Pharmacological treatment - Pulmonary rehabilitation- | X | X | X |
| Health-care resource consumption related to COPD, COPD | X | X | X |

| Study Visits | Visit 1 | Visit 2 | Visit 3 |
|--|----------|-----------------|-------------------|
| | Baseline | Follow-up | Follow-up 2 |
| Months | 0 | 6 (+/-1) | 12 (+/- 1) |
| exacerbations and adverse events: 
 • Drugs • hospitalization (inward and day hospital) • emergency room access • outpatient visits • GP visits • laboratory tests • clinical examinations | | | |
| Patient Reported Outcomes Questionnaires/scales | | | |
| TSQM-9 | X | X | X |
| MMRC (modified MRC dyspnea scale) | X | X | X |
| CAT | X | X | X |
| MMAS-4 (Morisky Medication-Taking Adherence Scale) | X | X | X |
| Brief Illness Perception Questionnaire | X | X | X |
| Awareness structured interview | X | X | X |
| S(AE) assessment | | X | X |

Table 1. Recorded variables.

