*** An exacerbation will be defined as an increase or new onset of more than 1 symptom (cough, sputum, wheezing, dyspnoea or chest tightness) with at least 1 symptom lasting at least 3 days and leading to patient's attending physician to initiate treatment with systemic steroids and/or antibiotics (moderate exacerbation) or hospital admission (severe exacerbation).*

Visit 2 (6+/-1 month), Visit 3 (12+/-1 month) are referred as being the current clinical practice in Italy for COPD patients management.

Data will be collected at inclusion visit, 6 (±1) and 12 (±1) month follow up.

The following questionnaires/scales/patient reported outcomes will be administered to patients. They are briefly described below.

- Treatment Satisfaction Questionnaire, 9 items (TSQM-9);
- Brief Illness Perception Questionnaire (BIPQ);
- Morisky medication Adherence Scale, 4 items (MMAS-4);
- COPD Assessment Test (CAT);
- Modified Medical Research Council Dyspnea Scale (MMRC).

Treatment Satisfaction Questionnaire for Medication, 9 items (TSQM-9)

Patient's self-reported satisfaction or dissatisfaction with pharmacological treatments can be measured using the Treatment Satisfaction Questionnaire for Medication (TSQM) Version 1.4, a validated instrument (45). The TSQM-9 was derived from the original version, and it has a total of 9 items with responses to nearly all items rated on a five-point or seven-point rating scale that provide scores on three scales: effectiveness (3 items), convenience (3

items) and global satisfaction (3 items) (9) . The original version also recorded information about side effects in 5 items (45). However in naturalistic studies, administering the TSQM with the side effects domain could provoke the physician to assess the presence or absence of adverse events in a way that is clinically atypical, carrying the potential to interfere with routine medical care.

The TSQM-9 domain scores (effectiveness, convenience and global satisfaction) will be calculated as recommended by the instrument authors (45,46). The TSQM-9 domain scores range from 0 to 100 with higher scores representing higher satisfaction on that domain.

The questionnaire will be completed by patients at enrolment, 6- and 12-month follow up visits.

Brief Illness Perception Questionnaire

The patient disease perception will be evaluated by the Brief Illness Perception Questionnaire

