Exacerbation is defined as "an increase or new onset of more than 1 symptom (cough, sputum, wheezing, dyspnoea or chest tightness) with at least 1 symptom lasting at least 3 days and leading to patient's attending physician to initiate treatment with systemic steroids and/or antibiotics (moderate exacerbation) or hospital admission (severe exacerbation)".

Patients with at least one exacerbation during observation period are those with "Did any exacerbation occur since the previous visit?" [F08_EXACERBATIONS.EX_Exacerbation_YN] = "Yes", considering the 6- and 12-month follow-up visits and the End of observation visit.

The **total number of exacerbations occurred during observation period per patient** will be computed as the sum of the number of the matrix rows filled in the following fields: [F08_EXACERBATIONS.Ex_exacer_1-10_Ons_date], considering the 6- and 12-month follow-up visits and the End of observation visit.

Hospitalizations for COPD, COPD exacerbations or COPD related adverse events during observation period

The **total number of hospitalizations not in ICU for each patient** will be the number of records in the matrix with "Patient admitted to intensive care unit?" [F10_RESOURCE_CONS. RES_Hosp_matrix_1_ICU_YN - RES_Hosp_matrix_10_ICU_YN] = "No", considering the visit form HEALTHCARE RESOURCE CONSUMPTION at the 6- and 12-month follow-up visits and the End of observation visit.

The **total number of hospitalizations in ICU for each patient** will be the number of records in the matrix with "Patient admitted to intensive care unit?" [F10_RESOURCE_CONS. RES_Hosp_matrix_1_ICU_YN - RES_Hosp_matrix_10_ICU_YN] = "Yes", considering the visit form HEALTHCARE RESOURCE CONSUMPTION at the 6- and 12-month follow-up visits and the End of observation visit.

The **total number of days of hospitalization not in ICU for each patient** will be the sum of the fields "Overall duration of admission (days)" [F10_RESOURCE_CONS. RES_Hosp_matrix_1_Adm - RES_Hosp_matrix_10_Adm], considering only the records referred to hospitalizations not in ICU (see above) at the 6- and 12-month follow-up visits and the End of observation visit.

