4.12 Exacerbations

Table 38. Exacerbations: patients' distribution

This table will provide:

- the distribution of patients by number of exacerbations per patient during observation period (see 'Computed variables' chapter);
- descriptive statistics (mean, median, standard deviation, quartiles, min, max) of number of exacerbations per patient during observation period (see 'Computed variables' chapter);
- the distribution of patients by exacerbation severity [[F08_EXACERBATIONS. Ex_Exacer_1_severity - Ex_Exacer_10_severity](#)];
- the distribution of patients by changes in COPD therapy due to exacerbations (i.e. "Any new therapy or any change to an ongoing one required*?") [[F08_EXACERBATIONS. Ex_Exacer_1_change - Ex_Exacer_10_change](#)].

Percentages will be computed out of the total number of patients evaluable for the FAS.

Table 39. Exacerbations: details

This table will provide:

- the distribution of exacerbations by exacerbation severity [[F08_EXACERBATIONS. Ex_Exacer_1_severity - Ex_Exacer_10_severity](#)];
- the distribution of exacerbations by changes in COPD therapy due to exacerbations (i.e. "Any new therapy or any change to an ongoing one required*?") [[F08_EXACERBATIONS. Ex_Exacer_1_change - Ex_Exacer_10_change](#)].

Percentages will be computed out of the total number of exacerbations occurred during observation period in FAS patients.

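### The SAP's on-study exacerbation count and any-exacerbation flag ignore severity, so any non-qualifying event entered as mild would be counted although the study definition covers only moderate and severe events

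*SAP*

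**What the plan says.** **Definition.** The footnote to Table 1 in Protocol section 9.3 (also in the Abstract) requires a symptom worsening that leads the treating physician to "initiate treatment with systemic steroids and/or antibiotics (moderate exacerbation) or hospital admission (severe exacerbation". SAP section 3, under the heading on exacerbations during the observation period, repeats this and ends with the same two tiers: "antibiotics (moderate exacerbation) or hospital admission (severe exacerbation". There is no third tier.

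**What is recorded.** The exacerbation row of Protocol Table 1 asks for onset and resolution dates and for "Severity (mild, moderate, severe". Neither document defines mild.

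**What is counted.** In SAP section 3 the total per patient "will be computed as the sum of the number of the matrix rows filled in the following fields"; the fields named are the onset dates of up to ten rows per form, taken over the two follow-up visits and the end-of-observation visit. A patient has at least one exacerbation if the item "Did any exacerbation occur since the previous visit" is answered Yes at any of these visits. Neither rule refers to severity, treatment or admission.

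**What is reported.** SAP section 4.12, Table 38, gives patients by number of exacerbations, summary statistics of that number, and "the distribution of patients by exacerbation severity". Table 39 gives "the distribution of exacerbations by exacerbation severity", with all on-study events in the full analysis set as denominator.

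**The concern.** A mild grade has no place in a definition whose lowest tier is already called moderate. The protocol allows the grade all the same, and the SAP derivation has no step that would keep such a row out of the total. The definition stands directly above the counting rule, but the rule does not apply it.

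The SAP filters rows elsewhere in the same chapter: hospitalizations are split on the intensive-care field, and therapies are selected on the purpose field. Here the severity field is collected and tabulated but not used.

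At stake are the on-study exacerbation figures with which Protocol section 9.7 undertakes to describe the population: the number per patient and the share of patients with any event. The planned quality control in SAP section 6 would not catch the problem, because for Table 38 it checks that the count follows the SAP algorithm, not that each row meets the definition.

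**Working it through.** The documents give no exacerbation count, rate or expected mild share, so there is no figure of the plan to reproduce.

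**Step 1. Event total.** Let T be the number of filled rows and m the share graded mild that do not meet the definition. Qualifying rows number (1-m)T, so the reported total exceeds the qualifying total by

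T / [(1-m)T] - 1 = m/(1-m).

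The value of m is an assumption, shown over a range:

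| Assumed m | Overstatement of event total |
|---|---|
| 0% | 0% |
| 5% | 0.05/0.95 = 5.3% |
| 10% | 0.10/0.90 = 11.1% |
| 20% | 0.20/0.80 = 25.0% |
| 30% | 0.30/0.70 = 42.9% |
| 40% | 0.40/0.60 = 66.7% |

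The mean per patient is the total divided by a fixed number of patients, so it is overstated by the same percentage.

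**Step 2. Share with at least one exacerbation.** The formula does not carry over. A patient with one mild and one moderate row is correctly flagged; only patients whose rows are all non-qualifying are wrongly flagged. Their number cannot exceed the number of non-qualifying rows, but it depends on how those rows cluster within patients, which m does not tell us.

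**Step 3. What the planned tables allow a reader to correct.**

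- *Event total and mean: recoverable.* Table 39 splits events by severity. Adding moderate and severe gives the total, and dividing by the full analysis set size in Table 1 gives the mean. This takes the recorded grade at face value.
- *Distribution, median, quartiles and SD per patient: not recoverable.* Table 38 does not cross the count with severity.
- *Share of patients with a moderate or severe event: only bounded.* If a patients have a moderate row and b a severe row, the number with either lies between max(a, b) and a + b, because one patient may appear in both. It would be exact only if each patient were classed once by worst grade, which SAP section 4.12 does not state.

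**Step 4. Effect of filtering on the label alone.** Suppose a fraction q of rows graded mild were in fact treated or admitted, and let m now be the share of all rows graded mild. True qualifying rows are then (1-m+mq)T. Counting all rows overstates by m(1-q)/(1-m+mq); keeping only moderate and severe rows understates by mq/(1-m+mq). A plain filter is therefore exact only if q = 0, which is why mild rows need to be queried first.

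**Step 5. Where the count is used.** The primary analysis (SAP section 4.3) does not involve it. The satisfaction models (section 4.9) use only covariates from enrolment, including the exacerbation number at that visit. The Table 37 correlations (section 4.11) use hospitalizations, emergency room accesses, visits, tests and therapies, not exacerbations. The on-study count therefore reaches only Tables 38 and 39.

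**The case against.** The strongest reply is that nothing is overstated if the plan is followed. In Protocol Table 1 the severity entry sits under an item footnoted with the full definition, and in the SAP the definition precedes both derivations. Read that way, a row is filled only for a qualifying event, and the overcount is zero. The count also runs on eCRF version 1.2, which is later than the protocol and whose severity options are not shown; that mild is offered there is inferred from the protocol table.

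This stands, and it makes the point conditional. A reader might infer that the reported numbers are inflated. The documents do not support that: they do not say that sites will enter non-qualifying events, and they give no value of m. They do leave room for it. The protocol lists the grade, and Tables 38 and 39 tabulate for each event whether a new or changed therapy was needed, an item that would hardly vary if every row already qualified. That makes such rows plausible; it does not show that they occur.

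A reader might also infer that the correct count cannot be recovered at all. Table 39 contradicts this for the event total and the mean. What is lost is the per-patient distribution and the exact share of patients.

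Finally, because mild is undefined, a row so graded may be a treated event judged by its symptoms, and dropping it on the label would remove a qualifying event. This also stands, and it shapes the fix.

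**Conclusion.** The inconsistency is in the text: a two-tier definition, a three-grade severity field, and a count and flag that use neither the grade nor the definition. Whether it changes any number depends on data entry. The event total and mean are overstated by m/(1-m), from zero at m = 0 to 66.7% at an assumed m of 40%, provided that every row graded mild is non-qualifying. The share of patients with any exacerbation may also be overstated, by an amount that the documents do not allow to be calculated. The effect is confined to the descriptive exacerbation tables; the primary objective, the satisfaction models and the resource-use correlations are untouched. This is a small correction, worth making because it is cheap.

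**What to change.** 1. In SAP section 3, reconcile the severity categories with the definition: state what mild means on the form and whether such an event can meet the study definition.
2. Before database lock, query each row graded mild against the treatment or admission recorded for it. The therapy log records the purpose of each therapy, and the resource form records the reason for each hospitalization, so no new data are needed.
3. Derive both the Table 38 count and the any-exacerbation flag from rows that meet the definition (moderate or severe after queries). Using the same rows for both also keeps the two figures consistent with each other.
4. Show the all-rows count alongside as a secondary line, so that the effect of the restriction is visible.
5. State in Table 38 whether a patient is classed once by worst grade or under every grade experienced.

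The cost is a short edit to one derivation, one added line in Table 38, and a query round limited to rows graded mild. If there are none, the results do not change.
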